5.2 APPENDIX 2 ANALYSIS DETAILS SPECIFIC TO TLR7 TREATMENT COMBINATION

TLR7 treatment combination arm specific analysis are listed in this appendix.

Immune Pharmacodynamics Biomarker Analysis: Markers of Humoral and Cellular Response

PD biomarker variables measured are listed in Table 7 below.

Table 7 List of Immune PD biomarker variables

Туре	Variable	Label	Unit
Transcriptional	TLR7	TLR7	delta Ct*
Transcriptional	OAS-1	OAS1	delta Ct*
Transcriptional	MX1	MX1	delta Ct*
Transcriptional	ISG-15	ISG15	delta Ct*
Serum soluble protein (cytokine)	IFN-α	IFN-alpha	ng/L
Serum soluble protein (cytokine)	IFN-γ	IFN-Gamma	ng/L
Serum soluble protein (cytokine)	IP-10	IP-10	ng/L
Serum soluble protein (cytokine)	TNF-α	TNF-alpha	ng/L
Serum soluble protein (cytokine)	IL-6	IL-6	ng/L
Serum soluble protein (cytokine)	IL-1	IL-1	ng/mL
Serum soluble protein (cytokine)	IL-10	IL-10	ng/L

^{*} delta Ct will be provided by the lab performing the analysis.

For each PD variable, descriptive statistics will be presented separately by treatment arm, appropriate TLGs will be produced as listed below.

- 1) Descriptive Statistics- N, Mean, SEM, SD, Median, Min, Max
- Geometric Mean and Change from baseline (baseline for the period) for each time point- tables and plots
- 3) Plot of Absolute Values over Time
- 4) Fold Change (FC) from BL for each time point tables and plots

Cytokine and Neopterin Variables:

Combination Therapies for CHB—F. Hoffmann-La Roche Ltd Statistical Analysis Plan WV41073

- Log10 for each variable at each time point
- Fold change from baseline for each time point based upon raw data
- Log10 fold change from baseline for each time point

Interferon-alpha:

 Systemic Interferon post dose is defined as interferon-alpha post dose > LLOQ pg/mL

Transcriptional Variables:

 Fold change from baseline for each time point calculated as 2**(Change from BL), eg, If change from BL=3 then fold change from baseline = 2**(3) =8.

PD data processing rules-

- Values below limit of quantification set to limit of quantification for cytokine and neopterin derived variables ('<' stripped from string).
- Raw value as transmitted to Roche for cytokine and neopterin variables
- Raw value is negative of original value as transmitted to Roche for transcriptional variables

Relationship between categorical HBsAq and PD Biomarkers:

The primary efficacy parameter is the incidence of HBsAg loss (that is <0.05IU/ml) at 24 weeks post EOT.

HBsAg will be categorized as;

HBsAg "Y": If HBsAg loss <0.05 IU/ml

HBsAg "N": If HBsAg loss >=0.05 IU/ml

The relationship between categorized HBsAg and PD biomarkers will be explored using logistic regression techniques where HBsAg category(Y/N) as response and PD biomarkers (IFN-alpha, IFN-Gamma, IP-10, TNF-alpha, IL6, IL10, IL1, Neopterin, TLR7, OAS1, MX1 and ISG15) and baseline quantitative HBsAg as independent variable. Stepwise selection option will be used to finalize the model. The independent variable will stay in the model which are significant at P<0.1.

The mathematical form of the model is as:

Response (Y/N) = IFN-alpha+ IFN-Gamma+ IP-10+ TNF-alpha+ IL6+ IL10+ IL1+ Neopterin+ TLR7+ OAS+, MX1+ ISG15+ BASE_HBsAg

Covariates will be checked for collinearity. Where collinearity occurs between two variables, only one of these variables will be included in the final model.

Combination Therapies for CHB—F. Hoffmann-La Roche Ltd Statistical Analysis Plan WV41073

An assessment of the goodness of fit of the model will be performed using the Pearson Chi-Squared Goodness of fit test, deviance test and visual inspection of index plots.

The odds ratio for PD biomarkers will be reported along with the 95% confidence interval. If required odds ratio will be reported by visit.

Estimand for TLR7 Treatment Combination:

The difference between proportions of HBsAg loss (qHBsAg <0.05 IU/mL) at week 24 follow-up in virologically suppressed adult CHB participants on established NUC therapy, with preserved liver function and without significant fibrosis/cirrhosis, treated with combination therapy [CpAM (600mg QD) +TLR7 (150mg QOD, 100mg QOD, 100mg QW) + NUC] versus NUC irrespective of adherence to IMP or whether prohibited medication and/or food has been taken.

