Appendix 12 Study Details Specific to siRNA (RO7445482) + TLR7 (RO7020531) + NUC Arm

[figure not shown]
An overview of short interfering RNA (siRNA) + toll-like receptor 7 (TLR7) + nucleos(t)ide NUC treatment arm is shown in Appendix 12-Figure 1.

Participants will receive RO7445482 (also known as DCR-HBVS; 200 mg Q4W) in addition to their background NUC therapy for the 48-week treatment period. RO7020531 (150 mg once every other day [QOD]) will be administered during Weeks 13-24 and Weeks 37-48 (i.e., 2 treatment cycles of 12 weeks' duration each and 42 doses of RO7020531 for each cycle). At the end of the treatment period, participants will continue NUC treatment during the follow-up unless the NUC discontinuation criteria have been met (see Section 6.8).

Approximately 30 participants will be randomized to this treatment arm.

If a 30% delta for HBsAg loss is observed at Week 48 (EOT) or follow-up Weeks 12 or 24 (primary endpoint) the treatment arm may be expanded to accrue additional efficacy and safety data, and to contribute to Phase 3 design planning. If a successful interim analysis is observed at Weeks 12 or 24, shorter treatment duration arms (12 and 24 weeks' duration) and/or a response-guided therapy (RGT) arm may be added.

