The relationship between categorized HBsAg and baseline covariates will be explored using logistic regression techniques where HBsAg category(Y/N) as response and baseline covariates- age, sex, race (or country), HBV genotyping, NME combination treatments, HBeAg status, baseline HBsAg, baseline ALT, baseline DNA as independent variable. Stepwise selection option will be used to finalized the model. The independent variable will stay in the model which are significant at P<0.1.

Covariates will be checked for collinearity. Collinearity will be examined through the Variance Inflation Factor and Tolerance. Where collinearity occurs between two variables, only one of these variables will be included in the final model. An assessment of goodness of fit of the model will be performed using the Pearson Chi-Squared Goodness of Fit test, deviance test and visual inspection of index plots.

The odds ratio for independent variables will be reported along with the 95% confidence interval. If required, odds ratio will be reported by visit.

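### SAP 5.2 picks TLR7 biomarkers stepwise from up to 13 candidates with perhaps 10 to 20 responders, so the 95% intervals of the markers it keeps cover well below 95%

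*SAP*

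**What the plan says.** SAP 5.2 (Appendix 2, TLR7 combination) gives the model for HBsAg loss at 24 weeks after end of treatment as "Response (Y/N) = IFN-alpha+ IFN-Gamma+ IP-10+ TNF-alpha+ IL6+ IL10+ IL1+ Neopterin+ TLR7+ OAS+, MX1+ ISG15+ BASE_HBsAg". That is 12 biomarkers and one baseline covariate.

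- Selection: "Stepwise selection option will be used to finalize the model", with the retention rule "The independent variable will stay in the model which are significant at P<0.1". No entry level is given.
- Reporting: "The odds ratio for PD biomarkers will be reported along with the 95% confidence interval". The analysis may also be repeated: "If required odds ratio will be reported by visit".
- The only control on the number of candidates is a collinearity rule: "Where collinearity occurs between two variables, only one of these variables will be included in the final model". Goodness-of-fit checks are planned too.
- The section sets no minimum number of responders, penalisation, internal validation or selection-adjusted interval. It does not say which biomarker time point or scale enters the model, or which arms are pooled.

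On arm size, Protocol Appendix 12 says "Approximately 30 participants will be randomized to this treatment arm". SAP 2.2 allows up to 30 more per arm after COVID-19 or force majeure disruption.

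SAP 4.3 relates HBsAg loss to eight baseline factors (age, sex, race or country, genotype, HBeAg status, HBsAg, ALT, HBV DNA) plus treatment. It uses the same approach ("Stepwise selection option will be used to finalized the model"), with the same P<0.1 retention rule and 95% intervals.

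SAP 2.1 and 4 call the study exploratory, with no formal testing and no multiplicity adjustment.

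**The concern.** Stepwise selection looks at all candidates and keeps those that happen to look strong. An ordinary 95% interval computed afterwards treats the chosen marker as if it had been fixed in advance. With about one event per candidate or fewer, the choice is driven largely by chance, and the interval does not show it.

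What is at stake is how the biomarker results read. A reader shown an odds ratio and a 95% interval for two or three surviving markers will take the interval at face value. The primary analysis and the interim and expansion rules are untouched, because they rest on HBsAg loss alone.

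**Working it through.** **The plan's own figure.** The documents give no operating characteristic for the stepwise model. The nearest figure is the 78% power in SAP 2.2 (3% control, 33% combination, 30 per arm, continuity-corrected two-sided chi-squared at 5%). The continuity correction gives an effective size n' = (nd − 1)²/(nd²) = (30 × 0.30 − 1)²/(30 × 0.09) = 64/2.7 = 23.7 per arm, and power 78.6%. The figure reproduces. It has no bearing on this model except to supply 33% as the planning response rate.

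**Events per candidate.**
- 33% loss: 0.33 × 30 = 9.9, and 9.9/13 = 0.76; 0.33 × 60 = 19.8, and 19.8/13 = 1.52.
- 10% loss (assumed, for range): 3/13 = 0.23 and 6/13 = 0.46.

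**Simple bound.** With 12 independent noise markers, the chance that at least one passes is 1 − 0.90¹² = 72% at P<0.1 and 1 − 0.95¹² = 46% at P<0.05.

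**Why the intervals fail.** A marker is kept only if its Wald |z| exceeds 1.645. Its 95% interval covers an odds ratio of 1 only if |z| is below 1.96. For a single noise marker in large samples, coverage given that it was kept is therefore (0.10 − 0.05)/0.10 = 50%. Choosing the strongest of several candidates, or a stricter entry level, lowers it further.

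**Simulation.** Twelve noise biomarkers plus a real baseline HBsAg effect (log odds ratio −1 per SD); score test to enter, Wald P<0.1 to stay; 1,000-1,500 runs per main scenario. The documents give neither the entry level nor the correlations, so both were varied. The block pattern has correlation 0.7 among the interferon-stimulated genes and 0.2-0.5 elsewhere. Chance that one final model keeps at least one noise marker:

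| Markers | Entry level | 30 patients, 10 responders | 60 patients, 20 responders |
|---|---|---|---|
| Independent | 0.10 | 65% | 71% |
| Independent | 0.05 | 50% | 47% |
| Block pattern | 0.10 | 54% | 56% |
| Block pattern | 0.05 | 40% | 37% |
| All correlated 0.5 | 0.10 | 50% | 49% |
| All correlated 0.8 | 0.10 | 30% | 31% |

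At correlation 0.8 and entry 0.05 the figure is about 20%. Entry at 0.15 gives the same results as 0.10. Pure backward elimination (60 patients, block pattern) gives 74%.

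**Coverage of an odds ratio of 1 by the intervals of kept noise markers.** Entry 0.10: 41-50% at 30 patients and 25-43% at 60. Entry 0.05: 35-38% and 10-15%. A separate simulation gave 12-62%. With very few responders (3 of 30, block pattern) coverage rises to 75-80%, still below 95%. The median ratio of upper to lower limit is about 23 at 30 patients and 5 at 60 (block pattern, entry 0.10). Restoring 95% coverage would take intervals 1.2-1.6 times as wide on the log scale.

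**Repeated by visit** (block pattern, assumed within-patient correlation 0.5, 600 runs), at least one noise marker at any visit:
- 2 visits: 78-82% (entry 0.10), 62-64% (entry 0.05).
- 4 visits: 91-95%, 77-81%.
- 6 visits: 98%, 88-91%.

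**Real signals** (block pattern, entry 0.10). A true odds ratio of 2 per SD is kept in 20% of runs at 30 patients and 44% at 60, with median reported odds ratios of 5.6 and 3.3.

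**Without selection.** One model per biomarker, adjusted for baseline HBsAg, with all 12 reported: coverage 96.8% (30 patients, 10 responders) and 95.3% (60, 20). Firth-penalised versions gave 97-99% in the separate simulation.

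**The case against.** The strongest reply is that this is an exploratory regression that drives no decision, in a study that disclaims testing and multiplicity control, and that SAP 5.2 gives descriptive output for the biomarkers in its Table 7 whether or not they are selected. That limits the consequence. It does not make an interval with 10-60% coverage a 95% interval.

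Several stronger readings are tempting, and the documents do not support them.

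- **That the model will usually report a chance biomarker.** For a single model this depends on the unstated entry level and the unknown correlations, and several plausible settings fall below half. Collinearity pruning would also remove some candidates. Thirteen is a maximum: neopterin is in the model but in neither SAP Table 7 nor the Protocol Appendix 12 cytokine panel. Protocol A12.14.1 makes IL-1, IL-10 and IFN-γ optional, although the schedule footnote lists them. With eight markers the simple bound is 1 − 0.90⁸ = 57% or 1 − 0.95⁸ = 34%.
- **That the intervals are far too narrow.** They are wide; the fault is their centre.
- **That the planned model breaks down.** The full 13-variable model separates completely in 61% of simulated datasets with 10 responders in 30 patients, but stepwise selection need not end in that model.
- **That SAP 4.3 is equally starved of events and its treatment odds ratio will be infinite.** Treatment is a covariate there, so more than one group is included. One arm plus control at 33% and 3% gives about 9.9 + 0.9 = 10.8 events for nine listed factors, and pooling arms gives more. An infinite estimate needs control to be in the model with no responders. That chance is 0.97³⁰ = 40% at 30 controls, but control keeps recruiting; at an assumed 65 it is 0.97⁶⁵ = 14%.
- **That these models are meant to choose markers for later trials.** Neither document says so.

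**Conclusion.** The point stands for SAP 5.2 as a fault in stated error bars. Selection from up to 13 candidates, on about 0.8-1.5 events per candidate at 33% response, keeps at least one noise marker in about 37-71% of single models when markers are independent to moderately correlated, and in 20-31% when strongly correlated. Repetition by visit raises this. The nominal 95% intervals of kept noise markers cover an odds ratio of 1 about 10-60% of the time.

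These figures assume that the model is fitted to the siRNA + TLR7 arm, the only live TLR7 arm, with 10 or 20 responders. The CpAM + TLR7 arm was terminated, and the control schedule in Protocol Appendix 7 has no cytokine or interferon-stimulated gene sampling, so pooling those arms would not clearly help.

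SAP 4.3 has the same fault in kind. Its size was not computed and depends on which arms are pooled. The change should be made, but nothing in the primary analysis depends on it.

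**What to change.** In SAP 5.2, drop stepwise selection. Fit one Firth-penalised logistic model per biomarker, adjusted for baseline log10 HBsAg. Add a treatment-arm term only if more than one arm with biomarker sampling is pooled; in a single arm it cannot be estimated. Report every marker's odds ratio and 95% interval, significant or not, labelled exploratory. State the arms, the biomarker time point and the scale, and settle whether neopterin is measured.

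In SAP 4.3, likewise report every baseline factor without selection. Use Firth penalisation so that the treatment odds ratio stays finite if control is included and has no responders.

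The cost is SAP wording only, with no new data or patients. Fewer markers will be called significant, and there will be no single multivariable model. Reporting all 12 corrects each interval but does not stop some from excluding 1 by chance (up to about 46% by the independence bound above). The reader will, however, see all 12 and can judge.

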5.3 APPENDIX 3 ANALYSIS DETAILS SPECIFIC TO SIRNA TREATMENT COMBINATION ARM

Effects of ADA on NMEs and/or IMP:

Relationship between ADA status, PK,safety, PD, and efficacy will be explored. The analysis detail will be given in final version of the statistical analysis plan.

Characterization of Injection Site Reactions

Adverse events that occur during or after study drug administration and are judged to be local and related to the SC study drug injection should be captured as a diagnosis (e.g., "injection site reaction)" on the Adverse Event eCRF and if judged to be systemic should be captured as a diagnosis "injection reaction (IR)"

All injection site reaction or injection reaction information will be listed. Injection Site Reactions (ISR) are usually immunological with delayed onset. ISR of onset 4 hours or more hours post dose called as modified ISR.

Grading of pre-defined ISR signs and symptoms (pain, erythema swelling and pruritus) should be based on DAIDS

The listing and summary table will be created for the ISR or IR and modified ISR. Summary table will include the number of participants (%) experiencing an event and the number of events.

Summaries are as follow:

- 1) Number of Injection site reaction/ injection reactions
- 2) Number of patients with modified ISR
- 3) ISR/IR with DAIDS grade >=3

Estimand for siRNA Treatment Combination:

The difference between proportions of HBsAg loss (qHBsAg <0.05 IU/mL) at week 24 follow-up in virologically suppressed adult CHB participants on established NUC therapy, with preserved liver function and without significant fibrosis/cirrhosis, treated with combination therapies;

- 1) siRNA (100 or 200mg Q4W)+ NUC,
- siRNA (200mg Q4W) + PEG-IFN (180ug QW)+ NUC,
- 3) siRNA (200mg Q4W) +CpAM (600mg QOD) +NUC,
- 4) siRNA (200mg Q4W) + TLR7 (150mg QOD, 100mg QOD, 100mg QW) + NUC

versus NUC, irrespective of adherence to IMP or whether prohibited medication and/or food has been taken.

5.4 APPENDIX 4 ANALYSIS DETAILS SPECIFIC TO PD-L1 LNA TREATMENT COMBINATION ARM

PD-L1 LNA treatment combination arm specific analysis are listed in this appendix.

The PD-L1 LNA treatment combination arms as follow:

- One treatment arm will evaluate a 24-week treatment duration where siRNA (200 mg Q4W) will be given during Weeks 1-24 and PDL1-LNA will be given during Weeks 13-24.
- A second treatment arm will evaluate a 36-week treatment duration where siRNA (200 mg Q4W) will be given during Weeks 1-24 and PDL1-LNA will be given during Weeks 25-36.

In both treatment arms, participants will receive their background NUC therapy for the duration of study treatment. At the end of the treatment period, participants will continue NUC treatment during the follow-up unless the NUC discontinuation criteria have been met

The detail analysis of the PBMC and FNA data will be cover in the next version of the statistical analysis plan.

Estimand for PDL1-LNA Treatment Combination:

The difference between proportions of HBsAg loss (qHBsAg <0.05 IU/mL) at week 24 follow-up in virologically suppressed adult CHB participants on established NUC therapy, with preserved liver function and without significant fibrosis/cirrhosis, treated with combination therapies

- 1) siRNA (200mg Q4W)+ PDL1-LNA + NUC, with 24 weeks treatment duration
- 2) siRNA (200mg Q4W)+ PDL1-LNA + NUC, with 36 weeks treatment duration

versus NUC, irrespective of adherence to IMP or whether prohibited medication and/or food has been taken.

The detail analysis of the PBMC and FNA data will be cover in the final version of the statistical analysis plan.

5.5 APPENDIX 5 PLANNED TREATMENT ARMS

An overview of the planned treatment arms is shown below.

Table 8 Planned Treatment Arms

Group	Treatment Arm	Arm Status	Number of Participants
1	NUC control	Ongoing	30 ^b
2	CpAM (600 mg) (RO7049389) + TLR7 (150 mg) (RO7020531) + NUC	Terminated ^c	~30
3	siRNA (100 mg) (RO7445482) + NUC	Ongoing	~30
4	siRNA (200 mg) (RO7445482) + NUC	Ongoing	~30
5	siRNA (200 mg) (RO7445482) + PEG- IFN (180 µg)+ NUC	Ongoing	~30
6	siRNA (200 mg) (RO7445482) + CpAM (600 mg) (RO7049389) + NUC	Terminated ^c	~30
7	siRNA (200 mg) (RO7445482) + TLR7 (150 mg) (RO7020531) + NUC	Ongoing	~30
8	siRNA (200 mg) (RO7445482) + PDL1- LNA (RO7191863) + NUC (24 weeks treatment duration)	Ongoing	~30
9	siRNA (200 mg) (RO7445482) + PDL1- LNA (RO7191863) + NUC (36 weeks treatment duration)	Ongoing	~30
TBD ^a	TBD		TBD

Abbreviations: NUC=nucleos(t)ide; TBD=to be determined.

^a Additional treatment arms may be added to the study.

^b Additional participants will be added as additional treatment arms are added to the study.

c Treatment arms terminated; patients performed early termination visit and entered in the safety follow-up period.

5.6 APPENDIX 6 MULTIPLE IMPUTATION TO HANDLE MISSING DATA DUE TO COVID-19 PANDEMIC OR DUE TO HYPOTHETICAL STRATEGY

Random Seed:

Random seed for MCMC procedure will be 21614 and MI procedure will be 22040. In case of non-convergence, the random seed will be updated by adding 18751 at each attempt until convergence of model happens.

Multiple Imputation (MI) and MAR Assumption:

When a categorical variable is derived from a continuous scale, for example, (SLOSS when HBSAG<0.05), HBSAG value will be log10 transformed to achieve normality, and then log10 transformed values will be imputed using MI method. To get the original scale, the imputed values will be back transformed. Then the categorical variable will be derived from the back transformed imputed value. Since the "<0.05" value is set to 0.05 for continuous scale in the database, as a conservative approach if the back transformed imputed value "<0.05" is categorized as the responder.

The MI procedure assumes that the data are missing at random (MAR). That is, for an outcome variable Y, the probability that an observation is missing depends only on the observed values of other variables, not on the unobserved values of the outcome variable Y. Statistical inference from the MI procedure is valid under the MAR assumption.

Imputation Algorithm:

It is reasonable to assume the missing values of the longitudinal data for an outcome variable follows a monotone missing pattern. In practice, the missing data of the outcome variable might have an arbitrary (non-monotone) missing data pattern. An extra step may be added to augment data into a monotone missing pattern. For the outcome variable (e.g., HBSAG at each visit), K 'complete' datasets can be generated in two steps: augmentation step and imputation step. K, the number of repetitions, is determined below.

Augmentation Step

For datasets with non-monotone missing data patterns the augmentation step will first impute enough values to augment the data into a monotonic missing pattern:

Markov Chain Monte Carlo (MCMC) will be applied to augment the data using PROC MI with the MCMC IMPUTE=monotone statement, assuming a multivariate normal distribution. The augmented data will be used in the subsequent imputation step to generate 'complete' datasets. Covariates included in the model are treatment, stratification factors, Baseline, and all post-baseline visits of the outcome variable according to the pre-specified order. Of note, categorical variables are included using the form of dummy variables.

Repeat the imputation process K=30 times using the procedure described above to form K=30 monotone missing datasets, where K is determined as described in "Repetition of

Combination Therapies for CHB—F. Hoffmann-La Roche Ltd Statistical Analysis Plan WV41073

imputations (K)."

Imputation Step

For missing data with monotone missing patterns, the choice of multiple imputation using a parametric regression model that assumes multivariate normality is appropriate.

The imputation step is described below:

- The imputation model for the missing data is a regression model, which
 controls for treatment, stratification factors,, Baseline, and all post-baseline visits
 of the outcome variable. The covariates included in the model and the order of
 these variables are consistent with the augmentation step.
- For each monotone missing dataset, using SAS PROC MI with MONOTONE REG model statement, the outcome variable at each post-baseline visit with missing values will be imputed sequentially with covariates constructed from their corresponding sets of preceding variables.
- A 'complete' dataset with imputed values for the missing data is generated after the augmentation and imputation steps are completed

Repetition of Imputations (K)

Repetition of imputations, K, must be determined in advance. In the usual clinical settings expecting less than 30% missing information, K=30 repetitions are deemed sufficient. When missingness exceeds 30%, depending on the power falloff tolerance level, number of repetitions may need to be increased. It is suggested that the number of repetitions (K) should be at least equal to the percentage of missing.

Derivation of Response Status and Non-Responder Imputation.

For each 'complete' dataset, the imputed post-baseline values will be back transformed to the original scale of the same precision as the observed data. Response status will be determined accordingly.

The imputed response status for missing due to reasons other than COVID-19 will be overridden by non-responder imputation to ensure that multiple imputation is only applied to missing due to COVID-19 and due to hypothetical strategy.

The only exception is that a subject will be categorized as a responder for the visit if the subject is a responder both before and after the specified visit window.

Analysis:

The statistical analysis will use the Cochran-Mantel-Haenszel (CMH) test adjusted by the stratification factors.

Also, binomial proportion and exact confidence interval for a proportion will be calculated for each treatment arm.

Analysis of Each Dataset

Combination Therapies for CHB—F. Hoffmann-La Roche Ltd Statistical Analysis Plan WV41073

For each of the K 'complete' datasets, the CMH test will be used to estimate the NME difference versus control and the corresponding standard error.

Also, for each of the K 'complete' datasets, binomial proportion and exact confidence interval for proportions will be calculated for each NME and control arm and the corresponding standard error.

Synthesis of Results for Statistical Inference

The results from the K 'complete' datasets will be synthesized using the SAS procedure PROC MIANALYZE, following Rubin's formula to derive the MI estimator of the treatment difference and proportions for the final inferences.

6. REFERENCES

Evolution of the food and drug administration approach to liver safety assessment for new drugs: current status and challenges [John R Senior, 2014]

